Once Screening procedures are completed and eligibility is confirmed, subjects will begin study treatment. A schematic of the study design is shown below in Figure 1.

Figure 1. Study Schema

All eligible subjects will initiate navitoclax orally (PO) once daily at the starting dose of 50 mg once daily (Cohort 1a) or at 100 mg or 200 mg once daily (Cohorts 1b, 2 or 3).

Cohort 1b will enroll approximately 80 subjects to ensure enrollment of approximately 70 subjects with prior exposure to ruxolitinib.

Cohort 1a

The dose of navitoclax may be increased after approximately 7 or more days to the next dose level provided the platelet count is $\geq 75 \times 10^9 / L$ up to a maximum dose of navitoclax 300 mg once daily.

Cohorts 1b, 2 or 3

- Baseline Platelet Count $> 150 \times 10^9$ /L: 200 mg once daily navitoclax starting dose
- Baseline platelet count $\leq 150 \times 10^9$ /L: 100 mg once daily navitoclax starting dose
 - The dose of navitoclax may be increased to 200 mg once daily after 7 days provided the platelet count is $\geq 75 \times 10^9/L$
- The dose of navitoclax should not exceed 200 mg once daily for the first 24 weeks of treatment. After the Week 24 disease assessment, the dose of navitoclax may be increased to 300 mg once daily at the discretion of the Investigator for subjects with sub-optimal spleen response defined as failure to achieve spleen volume reduction of at least 10% as assessed by imaging.

If a dose reduction below navitoclax 50 mg once daily is required, the dose of navitoclax may be reduced to 25 mg once daily following consultation with the AbbVie Therapeutic Area Medical Director/Scientific Director (TA MD/SD) (Section 6.1.5).

Subjects in Cohorts 1a, 1b or 3 will receive ruxolitinib administered orally twice daily (BID). Subjects in Cohort 1a and 1b receiving ruxolitinib at screening will continue at the current stable dose of ≥ 10 mg twice daily. Subjects in Cohorts 1b not receiving

ruxolitinib at the time of screening will receive ruxolitinib at a dose of 10 mg twice daily beginning on Day 1. Subjects in Cohort 3 will receive ruxolitinib at the individualized starting dose based on baseline platelet count as per the local approved ruxolitinib label. The dose of ruxolitinib may be reduced during the study to manage toxicities.

Subjects in Cohort 2 will receive Navitoclax monotherapy.

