For subjects enrolled in Cohort 3, ruxolitinib will be administered beginning on Day 1 at the individualized starting dose based on baseline platelet count as per local approved ruxolitinib label. The starting dose may be adjusted at investigator discretion as medically appropriate in consultation with the TA MD/SD with subsequent increase in dose as described in Appendix I.

Dose reductions should be implemented per the approved ruxolitinib local label; refer to the management of toxicities (Section 6.1.7).

Decisions regarding continued dosing, including the navitoclax or ruxolitinib dose level to be administered and increasing the dose of ruxolitinib higher than the starting dose, for individual subjects will be medically managed by the investigator in consultation with the AbbVie TA MD/SD.

On days with pre-dose pharmacokinetic sampling required, dosing of navitoclax and ruxolitinib will occur in the morning in the clinic to facilitate pharmacokinetic sampling.

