5.6.3 Selection of Doses in the Study

Thrombocytopenia observed during ruxolitinib treatment is generally reversible with dose reduction or dose interruption. Subjects enrolled in Cohort 1a and for subjects in Cohort 1b receiving ruxolitinib at the time of screening, will continue the stable dose of ruxolitinib ≥ 10 mg twice daily.

Subjects enrolled in Cohort 1b that are not receiving ruxolitinib at the time of screening will initiate ruxolitinib starting on Day 1 at the dose of 10 mg twice daily. The dose of 10 mg twice daily was selected for this population not receiving ruxolitinib based on the preliminary analysis of the combination of navitoclax and ruxolitinib in Study M16-109 (Cohort 1a). Of the 34 patients enrolled, 25 (74%) patients began study on doses of ruxolitinib > 10 mg twice daily. Of those 25 patients, 22 (88%) patients subsequently dose reduced ruxolitinib to ≤ 10 mg during study treatment. The primary reasons for ruxolitinib dose reductions are thrombocytopenia (55.9%) and anemia (11.9%). The preclinical data suggests that navitoclax may overcome JAK-2 resistance and therefore, re-sensitizing cells to JAK-2 inhibition from ruxolitinib. It is reported that a final titrated ruxolitinib dose of 10 mg twice daily induces spleen volume reductions and is associated with maximal symptom improvement. Therefore, a lower starting dose of ruxolitinib at 10 mg twice daily in patients not receiving ruxolitinib prior to entering the study, is rational when combining with navitoclax.

[figure not shown]
Subjects in Cohort 3 will receive ruxolitinib at the individualized starting dose based on baseline platelet count as per the local approved ruxolitinib label.

As a BCL-X_L inhibitor, navitoclax can also cause thrombocytopenia via intravascular apoptosis of platelets. AbbVie internal data indicates that the effect of navitoclax on platelet reduction is exposure-related but may be diminished upon continued administration. Accordingly, thrombocytopenia may occur with navitoclax upon exposure to sufficient navitoclax concentrations. Additionally, thrombocytopenia and anemia are the primary reason for ruxolitinib dose reductions.³⁴

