Appendix I. Dose Adjustment Guidelines for Thrombocytopenia and Neutropenia

- After navitoclax and/or ruxolitinib dose modification, platelet counts should be rechecked approximately 7 days or sooner as clinically applicable until at least 2 consecutive laboratory values indicate stable platelet count.
- If treatment is interrupted, recheck platelets approximately every 2 to 3 days until recovery of platelets to $\geq 50 \times 10^9/L$.
- Navitoclax Dose levels for daily dosing: 200 mg, 150 mg, 100 mg, 75 mg or 50 mg

Hematology Results	Action For Navitoclax	Navitoclax (All Cohorts)	Ruxolitinib Per Approved Local Label (Cohorts 1a, 1b, and 3)			
	Dose Modification for Thrombocytopenia					
Platelet counts ≥ 75 × 10 ⁹ /L	No change OR Increase dose	 Maintain current dose if platelet count ≤ 100× 10⁹/L Dose may be increased to 150 mg if the current dose of navitoclax is 100 mg and administered for at least 7 days and platelets have increased to > 100 × 10⁹/L. Dose may be increased to 200 mg if the current dose of navitoclax is 150 mg and administered for at least 7 days and platelets have increased to > 150 × 10⁹/L. 	 Reduce dose if current dose > 10 mg twice daily Maintain current dose if receiving 10 mg twice daily Dose may be increased to the label recommended dose if the current dose is lower than the label recommended dose and current dose of ruxolitinib has been administered for at least 7 days and platelet counts have remained stable at > 125 × 109/L with no other dose modifications of the regimen 			
Platelet counts ≥ 50 × 10 ⁹ /L to < 75 × 10 ⁹ /L	Dose reduction OR No Change	 Reduce navitoclax dose if platelets do not return to ≥ 75 × 10⁹/L OR Maintain current dose if counts are stable and no risk for bleeding per investigator discretion 	Consider dose reduction.			

EudraCT 2017-001398-17

- After navitoclax and/or ruxolitinib dose modification, platelet counts should be rechecked approximately 7 days or sooner as clinically applicable until at least 2 consecutive laboratory values indicate stable platelet count.
- If treatment is interrupted, recheck platelets approximately every 2 to 3 days until recovery of platelets to $\geq 50 \times 10^9/L$.
- Navitoclax Dose levels for daily dosing: 200 mg, 150 mg, 100 mg, 75 mg or 50 mg

Hematology Results	Action For Navitoclax	Navitoclax (All Cohorts)	Ruxolitinib Per Approved Local Label (Cohorts 1a, 1b, and 3)		
	Dose Modification for Thrombocytopenia				

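### Appendix I tells sites to reduce ruxolitinib above 10 mg twice daily at any platelet count of 75 × 10⁹/L or more, which conflicts with the stable-dose instruction for Cohorts 1a and 1b and with its own table

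*Protocol*

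**What the plan says.** Protocol Appendix I gives dose actions by platelet band. The top band is "Platelet counts ≥ 75 × 10 ⁹ /L", with no upper bound. Its navitoclax action is "No change OR Increase dose". Its ruxolitinib cell, in a column titled as following the approved local label, has three bullets:

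- The first is an unconditional instruction: "Reduce dose if current dose > 10 mg twice daily".
- The second keeps subjects who are already at that threshold where they are.
- The third is permissive: "Dose may be increased to the label recommended dose if the current dose is lower than the label recommended dose". It is open only after 7 days or more on the present dose, with a steady count above 125 × 10⁹/L and nothing else in the regimen modified.

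For platelets from 50 to below 75 × 10⁹/L, the ruxolitinib cell asks only that a reduction be considered. Below 50 × 10⁹/L it calls for interruption per the label.

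Section 5.1 says: "Subjects in Cohort 1a and 1b receiving ruxolitinib at screening will continue at the current stable dose of"; the minimum it then gives is 10 mg twice daily. It adds that ruxolitinib may be reduced to manage toxicity. Section 5.5.1 repeats the stable-dose instruction for Cohorts 1a and 1b. For Cohort 3 it says "ruxolitinib will be administered beginning on Day 1 at the individualized starting dose based on baseline platelet count as per local approved ruxolitinib label". It then directs that reductions follow the approved local label and refers to the toxicity section (6.1.7). Section 6.1.7 applies its guidelines to all subjects unless the sponsor's medical or scientific director has approved otherwise, and 6.1.7.1 sends the reader to Appendix I.

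**The concern.** Ruxolitinib is the background drug in Cohorts 1a, 1b and 3. Consider a subject above 10 mg twice daily with a normal platelet count and no toxicity. The design and dosing sections give no reason to change the dose, while the first Appendix I bullet, read literally, says to lower it. No text says which passage governs. Two sites could therefore manage the same subject differently and each point to the protocol.

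At stake is whether background exposure is defined consistently in three single-arm cohorts. The ambiguity also reaches the SAP, which measures ruxolitinib dose intensity against the protocol-specified schedule (SAP 6.4).

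**Working it through.** This is mainly a comparison of text. The arithmetic only shows scale.

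**1. Who falls in the row.** The condition is platelets ≥ 75 × 10⁹/L with no upper limit (Appendix I). Inclusion criterion 15 requires ≥ 100 × 10⁹/L in Cohorts 1a, 1b and 3. Since 100 ≥ 75, every eligible combination subject meets the condition at entry. As printed, the row is not confined to subjects with thrombocytopenia.

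**2. Appendix I against the dosing text, for a subject above 10 mg twice daily without toxicity.**

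| Cohort | Sections 5.1 and 5.5.1 | Appendix I, first bullet | Conflict |
|---|---|---|---|
| 1a | Continue stable dose; reduce for toxicity or per label | Reduce | Yes |
| 1b, on ruxolitinib at screening | As 1a | Reduce | Yes |
| 1b, not on ruxolitinib at screening | Start at 10 mg twice daily | Not triggered at 10 mg | No |
| 3 | Start at label dose; later reductions per label | Reduce | With the label-based reduction rule, not with the starting dose |

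**3. Within the cell.** Take a subject above 10 mg twice daily but below the label dose, with platelets stable above 125 × 10⁹/L. The first bullet says reduce; the third permits an increase. Likewise, wherever the label dose exceeds 10 mg twice daily, a subject raised to it under the third bullet immediately meets the first. (The label is not in the documents, so how often this arises is unknown.)

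**4. Across rows.** Reading down the ruxolitinib column for a dose above 10 mg twice daily:

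- ≥ 75: reduce
- 50 to < 75: consider reducing
- < 50: interrupt

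The instruction is firmer in the highest band than in the one below it.

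**5. Scale.** Section 5.6.3 reports that, of 34 Cohort 1a subjects, "25 (74%) patients began study on doses of ruxolitinib" above 10 mg twice daily, and that 22 of these later came down to 10 mg or less.

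- 25/34 = 73.5% (stated as 74%)
- 22/25 = 88.0% (stated as 88%)
- 34 − 25 = 9 subjects; 9/34 = 26% did not start above 10 mg twice daily

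Both stated figures reproduce. So 25 of 34 entered on a dose to which the two sets of instructions give different answers.

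**6. Where the analysis is touched (illustration only).** SAP 6.4 sets RDI = ODI/PDI × 100%, with the planned dose taken from the protocol schedule. Appendix I names no target for the reduction. Assume an entry dose of 15, 20 or 25 mg twice daily (tablet strengths in protocol Table 4) and the lower dose taken throughout:

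| Entry dose (mg twice daily) | RDI if reduced to 10 mg, planned dose = entry dose | RDI if reduced by one 5 mg step, planned dose = entry dose |
|---|---|---|
| 15 | 10/15 = 67% | 10/15 = 67% |
| 20 | 10/20 = 50% | 15/20 = 75% |
| 25 | 10/25 = 40% | 20/25 = 80% |

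If the planned dose is instead the reduced Appendix I dose, RDI is 100% in every line. No sample size, confidence interval or error rate changes.

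**The case against.** The strongest defence is context. Appendix I is titled as guidance for thrombocytopenia and neutropenia, and the row sits under a thrombocytopenia heading. The navitoclax increase bullets speak of counts that have risen, which suggests recovery after an event. The ruxolitinib column is titled as following the local label, and Sections 5.5.1 and 6.1.7 leave individual dose decisions to the investigator in consultation with the sponsor. A site would most naturally open this table after a platelet event. This makes the literal reading less likely in practice. It does not say which passage governs, and the bullet states its own 10 mg threshold without reference to the label. The table was read from PDF, so a lost qualifier cannot be excluded, but the bullets read as complete.

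Several stronger readings are tempting and are not supported:

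- **That Cohort 3's starting dose is contradicted.** Section 5.5.1 sets only a start and itself points to Appendix I for later increases. A modification table that acts later does not contradict a starting dose.
- **That the row catches most combination subjects.** The 74% comes from Cohort 1a alone. No share is given for Cohorts 1b or 3, and Cohort 1b subjects started at 10 mg twice daily are outside the bullet.
- **That Cohort 1a's Week 24 result was affected by this text.** Cohort 1a was fully enrolled by 10 April 2019 and its Week 24 spleen data are given in Section 3.4 alongside a 28 February 2020 data date, whereas the synopsis reviewed is dated 04 October 2021. Whether earlier amendments carried the same row cannot be seen.
- **That sites followed the row.** The 22 reductions do not show this; Section 5.6.3 gives thrombocytopenia and anemia as the main reasons for ruxolitinib reductions.

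**Conclusion.** The protocol is internally inconsistent. As printed, the first ruxolitinib bullet in the top platelet band conflicts with the stable-dose instruction for Cohort 1a and for Cohort 1b subjects on ruxolitinib at screening, and with the rule, covering Cohort 3 as well, that reductions are for toxicity or per label. It also conflicts with the third bullet in its own cell and sits oddly against the softer wording of the next lower band. This is a clash between stated rules, not missing detail.

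The only scale the documents give is 25 of 34 (74%) in Cohort 1a starting on a dose to which the conflict applies. A reader might infer a bias in the primary spleen endpoint or a known difference between sites. Neither can be shown: how sites acted cannot be determined, and no effect on response is quantified. The conclusion rests on the bullet being complete as it reads. Confidence is medium, and the point should be fixed because conflicting dosing instructions are cheap to remove.

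**What to change.** Reconcile the Appendix I ruxolitinib cell for platelets of 75 × 10⁹/L or more with Sections 5.1 and 5.5.1, with its own column title, with the increase bullet in the same cell and with the 50 to < 75 row, so that one instruction governs each situation. Which instruction that should be is a clinical decision for the sponsor, and no view is given here. Once it is settled, the planned ruxolitinib dose used in SAP 6.4 should be checked against the reconciled text.

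The cost is a protocol clarification. No sample size, endpoint definition or planned interval estimate needs to change.

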# 1.0 Introduction

This statistical analysis plan (SAP) describes the statistical analyses to be conducted by the Data and Statistical Science Department for Navitoclax (ABT-263) Study M16-109. The study examines the efficacy and safety of Navitoclax alone or in combination with Ruxolitinib in subjects with primary Myelofibrosis (PMF) or secondary MF (Post Polycythemia Vera [PPV-MF] or Post Essential Thrombocythemia [PET-MF]).

This SAP provides details to further elaborate statistical methods as outlined in the study protocol (amendment 11). It will not be updated in case of administrative changes or amendments to the protocol unless if the changes impact the analysis. In addition to this SAP, Statistical Programming Plan (SPP) will document details to guide the statistical programming work.

Unless noted otherwise, all analyses will be performed using SAS Version 9.4 (SAS Institute Inc., Cary, NC 27513) or later under the UNIX operating system.

# 2.0 Study Design and Objectives

[figure not shown]
# 2.1 Objectives and Hypotheses

The primary objective of the study is to:

• Evaluate the effect of navitoclax alone or in combination with ruxolitinib on spleen volume.

The secondary objectives of the study are:

- To assess the effect of navitoclax alone or in combination with ruxolitinib on total symptom score (TSS) as assessed by the Myelofibrosis Symptom Assessment Form (MFSAF) version 4.0 diary.
- To evaluate the effect of navitoclax alone or in combination with ruxolitinib on bone marrow fibrosis.

- To determine the rate of anemia response associated with navitoclax alone or in combination with ruxolitinib.
- To describe the safety profile and PK profile observed with navitoclax alone or in combination with ruxolitinib.

The exploratory objectives of the study are:

- To evaluate the effect of navitoclax alone or in combination with ruxolitinib on the onset, magnitude, and duration of disease response, including effects on spleen and anemia.
- To evaluate the effect of navitoclax alone or in combination with ruxolitinib on measures of health-related quality of life including total symptom score, fatigue, and physical functioning.
- To evaluate the effect of navitoclax alone or in combination with ruxolitinib on overall survival and progression free survival.
- Exploration of biomarkers predictive of navitoclax activity and response may be performed.

# 2.2 Study Design Overview

[figure not shown]
This is a Phase 2, multicenter, open-label study designed to evaluate the tolerability and efficacy of navitoclax alone or in combination with ruxolitinib in subjects with primary or secondary myelofibrosis (PPV-MF, PET-MF). Subjects enrolled in Cohort 1a must have received ruxolitinib therapy for at least 12 weeks and currently be on a stable dose of  $\geq 10$  mg BID of ruxolitinib. For Cohort 1b subjects must have received treatment with ruxolitinib for at least 24 weeks and currently on stable dose of  $\geq 10$  mg BID of ruxolitinib or had < 24 weeks of ruxolitinib with evidence of disease progression. For Cohort 2, subjects must have received prior treatment with a JAK-2 inhibitor. For Cohort 3, subjects must not have received prior treatment with a JAK-2 inhibitor, BH3 mimetic or BET inhibitor.

Approximately 174 subjects at approximately 135 sites globally will be enrolled in the following cohorts:

- Cohort 1a: 34 subjects
- Cohort 1b: approximately 80 subjects will be enrolled to ensure approximately 70 subjects with prior Ruxolitinib exposure.
- Cohort 2: approximately 30 subjects
- Cohort 3: approximately 30 subjects

Figure 1 is the study schema per protocol.

Figure 1. Study Schematic

Subjects will continue their treatment until end of clinical benefit, unacceptable toxicity or subject meets other protocol criteria for discontinuation (whichever occurs first). All subjects will have a treatment completion visit (TCV) performed when treatment is discontinued.

Response and progression will be assessed by the Investigator based on the International Working Group-Myeloproliferative Neoplasms Research and Treatment and European Leukemia Net (IWG-MRT/ELN). Spleen volume will be assessed independently by a central imaging vendor and interpretations will be transmitted to investigators, as available, and will be utilized in determining response and progression.

# 2.3 Treatment Assignment and Blinding

This is an open-label and non-randomized study.

[figure not shown]
## 2.4 Sample Size Determination

The primary endpoint for each Cohort of the study is SVR35W24 (at least 35% reduction in spleen volume by MRI/CT at Week 24 from baseline). Approximately 174 subjects in total will be enrolled in this study across all Cohorts. Point estimate and exact 95% confidence interval of SVR35W24 rate corresponding to observed number of subjects with SVR35W24 are presented in Table 1 for each Cohort.

Table 1. Point Estimates and 95% CI of Rate of SVR35W24 Corresponding to Observed Number of Subjects with SVR35W24

	Sample Subject		cts with (SVR 35w24 Rate)	Exact 95% CI		
Cohort		Number of Subjects with SVR 35W24		Lower Limit (%)	Upper Limit (%)	Half Width of CI
1a	34	16	47.06	29.78	64.87	17.55
1a	34	18	52.94	35.13	70.22	17.55
1a	34	20	58.82	40.70	75.35	17.33
1a	34	22	64.71	46.49	80.25	16.88
1b	70	32	45.71	33.74	58.06	12.16
1b	70	34	48.57	36.44	60.83	12.19
1b	70	36	51.43	39.17	63.56	12.19
1b	70	38	54.29	41.94	66.26	12.16
2 or 3	30	12	40.00	22.66	59.40	18.37
2 or 3	30	14	46.67	28.34	65.67	18.67
2 or 3	30	16	53.33	34.33	71.66	18.67
2 or 3	30	18	60.00	40.60	77.34	18.37

The study with 34 subjects in Cohort 1a, 70 subjects in Cohort 1b, 30 subjects in Cohort 2 and 30 subjects in Cohort 3 showed in the above table, respectively, a reasonable precision for estimate of SVR35W24. Also, if true probability of experiencing a serious

adverse event (SAE) due to the study treatment is 10%, then the probability of observing at least one SAE in 34 subjects is more than 97% in Cohort 1a; the probability of observing at least one SAE in 80 subjects is more than 99% in Cohort 1b; the probability of observing at least one SAE in 30 subjects is more than 95% in Cohort 2 and 3, respectively. Therefore, from safety assessment prospective the proposed sample size is adequate.

# 3.0 Endpoints

## 3.1 Primary Endpoint

SVR35W24, at least 35% reduction in spleen volume at Week 24 from baseline as measured by MRI or CT according to the IWG criteria.

# 3.2 Secondary Endpoint(s)

[figure not shown]
Secondary efficacy endpoints are as follows:

- TSS50W24, at least 50% reduction in TSS at Week 24 from baseline as measured by MFSAF version 4.0^2
- Anemia response
- Change in bone marrow fibrosis grade according to the European consensus grading system^3

# 3.3 Additional Efficacy Endpoint(s)

Exploratory efficacy endpoints are as follows:

- SVR35, at least 35% reduction in spleen volume from baseline as measured by MRI or CT according to the IWG criteria at any time point during study
- Duration of SVR35
- At least 50% reduction in palpable spleen length from baseline
- At least 50% reduction in TSS at any time point from baseline as measured by MFSAF v4.0

- Change in TSS and each MFSAF (v4.0) score from baseline
- Duration of anemia response
- Change in EORTC-QLQ-C30 score from baseline
- Change in PROMIS score from baseline
- Overall response per modified IWG criteria
- Progression Free Survival (PFS) per modified IWG criteria
- Overall survival (OS)
- 10%, 20%, and 30% Reduction in spleen volume from baseline as measured (SVR10, SVR20, and SVR30) by MRI/CT at any time point during study
- 10%, 20%, and 30% Reduction in spleen volume from baseline as measured (SVR10, SVR20, and SVR30) by MRI/CT at Week 24
- Post-baseline PRBC transfusion independence

[figure not shown]
